## 7.3 PHARMACODYNAMIC ASSESSMENTS

Blood samples for PD analyses will be collected at baseline and at the timepoints specified in the schedule of events tables in [Appendix A](#). Whole blood will be collected for immunophenotyping and analyzed by flow cytometry to enumerate immune cell subsets.. All immunophenotypic PD data will be summarized by dose and sampling times. Summary statistics in each table will include arithmetic mean, geometric mean, % coefficient of variation, SD, median, minimum, and maximum. All PD assessments will be analyzed for the PK & Biomarker analysis set.

### 7.3.1 IMMUNOPHENOTYPING OF CELL POPULATIONS ASSESSMENT

Whole blood will be collected for flow cytometry analysis to evaluate and quantify T, B, natural killer, and Tregs cells. Only data from Immunophenotyping flow cytometry samples that pass Merck sample quality review (Pass/Fail criteria documented in Merck ELN) will be transferred from PPD for analysis. All reportable cell populations and calculations that will be performed are defined [Table 8](#).

Immunophenotyping PD analyses listed in [Table 8](#) will be summarized by dose group at each timepoint, except for maximum fold change from baseline. The maximum absolute change from baseline and maximum fold-change from baseline may be calculated for each cell population. Individual subject level immunophenotypic PD data will be provided in supplemental by-subject listings. Supplemental time course immunophenotyping profile figures will be developed for each cell population type assessed showing mean immunophenotyping parameter level with SD error bars versus time (actual day of collection), doses and dosing regimen. Baseline used in calculations will be defined as the average level of the screening sample and the Day 1 pre-dose sample. If in the event only one sample was available, that sample would be utilized to determine baseline. CD25 mean fluorescence intensity on Tregs will be analyzed at each timepoint.

**Table 8. Parameters and Analyses to be Reported From the Immunophenotyping Panel**

Cell Population	Antigen Markers	Parameter	Absolute Count (cell/µl)	Percentage of Lymphocytes	Percent of Parent Cell Type a	Absolute Change From Baseline b	Fold Change From Baseline c	AUC of Absolute Change From Baseline d
Total T lymphocytes	CD45 + CD14  CD3 +	Absolute counts and relative percentage of cell subsets of interest	Output from PPD Inc	Output from PPD Inc	no	yes	yes	yes
Helper T lymphocytes	CD45 + CD14  CD3 + CD4 + CD8 		Output from PPD Inc	Output from PPD Inc	no	yes	yes	yes
Cytotoxic T lymphocytes	CD45 + CD14  CD3 + CD4 + CD8 +		Output from PPD Inc	Output from PPD Inc	no	yes	yes	yes
B lymphocytes	CD45 + CD14  CD3 + CD20 + CD56 		Output from PPD Inc	Output from PPD Inc	no	yes	yes	yes
Natural killer cells	CD45 + CD14  CD3 + CD20  CD56 +		Output from PPD Inc	Output from PPD Inc	no	yes	yes	yes
Tregs	CD45 + CD14  CD3 + CD4 + CD8  CD127 -/dim FoxP3 +		Output from PPD Inc	Output from PPD Inc	yes c	yes	yes	yes
CD25 Total Tregs	CD45 + CD14  CD3 + CD4 + CD8  FoxP3 + CD25 +		Output from PPD Inc	Output from PPD Inc	yes c	yes	yes	yes

AUC = area under the curve; N/A = not applicable; Tconv = conventional T cell; Treg = regulatory T cell  
Equations:

a Percent of Parent Cell Type: 
$$\frac{\text{Absolute number of Tregs}}{\text{Absolute number of helper T lymphocytes}}$$

Cell Population	Antigen Markers	Parameter	Absolute Count (cell/ $\mu$ l)	Percentage of Lymphocytes	Percent of Parent Cell Type a	Absolute Change From Baseline b	Fold Change From Baseline c	AUC of Absolute Change From Baseline d
b Absolute Change in Cell Count from Baseline: $Absolute\ number\ of\ Cell\ Type\ at\ Time\ x - Absolute\ number\ of\ Cell\ Type\ at\ Baseline$								
c Fold Change from Baseline: $\frac{Absolute\ number\ of\ cell\ type\ at\ Time\ x}{Absolute\ number\ of\ cell\ type\ at\ Baseline}$								
d Calculated from absolute change in cell count from baseline time course profile								

## 8 BIOMARKER ANALYSES

Relationships of biomarker parameters (e.g., baseline values, changes from baseline) to efficacy, safety, and PK parameters will be explored. Relationships and associated data that are determined to be of interest will be summarized. Biomarker analysis will be analyzed for the PK & Biomarker analysis set.

Listings and descriptive statistics (n, mean, median, SD, CV%, minimum, and maximum) will be provided by treatment group for each biomarker specified in **Table 9** as follows:

- Baseline values
- Values at each post-baseline visit
- Absolute change from baseline at each post-baseline visit
- Fold Change from baseline at each post-baseline visit

In addition, the following figures will be generated for sCD25, IL-5, IFN- $\gamma$ , IL1-B, IL-2, IL-4, IL-6, IL-8, IL-10, IL12p70, IL-13, TNF-a, and FOXP3, and CD4:

- Mean plot of absolute level aggregated and separated by treatments
- Mean plot of fold change from baseline aggregated and separated by treatments
- Mean plot of absolute change from baseline aggregated and separated by treatments

All other biomarker analysis will be included in a separate Translational SAP.

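### SAP Section 8 averages biomarker fold changes arithmetically, so the expected value is above 1 when nothing changes; Section 7.3 asks for geometric means of absolute changes, which can be zero or negative

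*SAP*

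**What the plan says.** **Biomarkers (SAP Section 8).** The plan states: "Listings and descriptive statistics (n, mean, median, SD, CV%, minimum, and maximum) will be provided by treatment group for each biomarker". The Table 9 markers are fecal calprotectin, hs-CRP, sCD25, the cytokines and the two TSDR assays. One of the listed quantities is "Fold Change from baseline at each post-baseline visit". For every marker except fecal calprotectin and hs-CRP there is also a "Mean plot of fold change from baseline aggregated and separated by treatments".

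**Immunophenotyping (SAP Sections 7.3 and 7.3.1, Table 8).** Here the statistics are broader: "Summary statistics in each table will include arithmetic mean, geometric mean, % coefficient of variation, SD, median, minimum, and maximum". The Table 8 analyses "will be summarized by dose group at each timepoint, except for maximum fold change from baseline". Table 8 covers fold change, absolute change and "AUC of Absolute Change From Baseline" for every cell population, Tregs included.

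**General conventions (SAP Section 4.1).** Laboratory analytes believed to be roughly log-normal receive a geometric mean and CV in addition to the usual statistics. Another bullet, introduced with safety and efficacy results, allows differences from baseline to be computed on the raw scale or on the log scale, depending on the parameter. Neither convention lists the analytes it applies to.

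**The concern.** The two sections have their statistics the wrong way round for part of what they cover. A ratio to baseline calls for averaging on the log scale, and Section 8 does not ask for that. A difference from baseline can be zero or negative, so it has no geometric mean in general, yet Section 7.3 asks for one.

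Sections 7.1 and 7.3 name arithmetic and geometric means separately, so the unqualified mean in Section 8 reads as arithmetic. The SAP also treats similar quantities differently: flow-cytometry Treg fold change gets a geometric mean, while fold change in the TSDR FOXP3 assay, also labelled as Treg cells, does not.

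What is at stake is interpretation. Protocol Section 1.4 speaks of Treg response in terms of 2-fold expansion. Section 1.3 supports selectivity partly by the lack of meaningful cytokine change. SAP Section 13 lists biomarker descriptive statistics among the analyses that may go to the DRC. A mean fold-change plot drifting above 1 could be read as cytokine release when it is only noise.

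**Working it through.** The plan states no figure on this point, so there is none to reproduce.

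**Inputs.** Group sizes per cohort are 8 PT101 and 2 placebo (Protocol Section 9.1). The within-subject SD of the log ratio, *s*, is not given, so a range is assumed.

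**1. Arithmetic mean fold change under no change**

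- Simplest case: one subject doubles and one halves. The arithmetic mean is (2 + 0.5)/2 = 1.25; the geometric mean is √(2 × 0.5) = 1.00.
- If ln(post/baseline) is normal with mean 0 and SD *s*, the expected arithmetic mean is exp(s²/2). The chance that the mean of 8 subjects exceeds 1 comes from 400,000 simulated groups of 8.

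| Assumed *s* | exp(s²/2) | P(mean of 8 > 1) |
|---|---|---|
| 0.2 | 1.02 | 0.60 |
| 0.4 | 1.08 | 0.68 |
| 0.5 | 1.13 | 0.72 |
| 0.7 | 1.28 | 0.78 |
| 1.0 | 1.65 | 0.84 |

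The back-transformed mean log ratio had a simulated median of 1.00 at every SD.

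- The direction does not depend on log-normality. For any exchangeable positive pair (baseline B, post X), E[X/B] = E[(X/B + B/X)/2] ≥ 1.
- A rough anchor for Tregs comes from the sample-size statement: ratio of 2, one-sided alpha 0.1, 80% power, 8 versus 2. Taken as a two-sample comparison of logs, it implies s = ln 2 / [(1.2816 + 0.8416) × √(1/8 + 1/2)] = 0.6931/1.6786 = 0.41. Then exp(0.41²/2) is about 1.09. The actual variance assumption is redacted, and this anchor concerns Tregs, not cytokines.

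**2. Geometric mean of absolute change**

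With no true change and changes symmetric about zero, each value is zero or negative with probability about 0.5. The chance that at least one of *n* is zero or negative is 1 − 0.5ⁿ:

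- placebo, n = 2: 1 − 0.25 = 0.75
- PT101, n = 8: 1 − 0.0039 = 0.996

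The same reasoning applies to the AUC of absolute change if that is also symmetric about zero. A negative value leaves the geometric mean undefined; an exact zero makes it zero or undefined, depending on the software.

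The problem remains with a real effect. For a true 2-fold rise, the chance per subject is Φ(−ln 2/s). Among 8 subjects, at least one value is zero or negative with probability 0.29 at s = 0.4, 0.50 at s = 0.5 and 0.76 at s = 0.7.

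**3. CV% of absolute change**

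CV% divides the SD by the mean. Under no change the mean is near zero, so the ratio can take almost any size and either sign. Sections 7.3 and 8 both request it for absolute change.

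**The case against.** The strongest reply has four parts.

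- **Section 4.1 already supplies the method.** A back-transformed log difference is a ratio to baseline, and log-normal analytes are promised a geometric mean. This stands in part: the SAP accepts the principle. But the log-scale bullet speaks of safety and efficacy results, no biomarker is assigned to either convention, the geometric mean is an addition rather than a replacement, and nothing changes the Section 8 plots or exempts change scores.
- **The bias is mild in use.** With a true fold change θ, the expected arithmetic mean is θ·exp(s²/2), so the ratio of PT101 to placebo is unaffected if *s* is equal in both arms. Medians, ranges and listings are also provided, and no test or decision threshold is attached. This stands. The exposed reading is a single arm against 1, which is hard to avoid with only 2 placebo subjects per cohort.
- **The larger SDs have no source in the documents.** This stands; the table is a range, not an estimate.
- **The undefined statistic is one cell.** The arithmetic mean, SD, median and range sit beside it and are valid. This also stands.

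**Conclusion.** Both parts hold, as a minor point about descriptive secondary and exploratory summaries. Section 8 as written uses a statistic whose expected value under no change is above 1, by 2% to 65% for assumed log-ratio SDs of 0.2 to 1.0. Section 7.3 as written asks for a statistic that will usually fail under no change: about 75% of the time with 2 subjects and 99.6% with 8, assuming independent subjects and symmetric changes.

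Three stronger readings are tempting, and the documents do not support them.

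- *Both arms will show a rise in noisy cytokines.* The shift is an expectation. In a group of 8 the mean exceeds 1 with probability 0.60 to 0.84 over the same range of SDs.
- *The Treg contrast between PT101 and placebo is understated.* That would require computing the geometric mean on positive changes only. The SAP states no such handling, and a blank cell is as likely.
- *The Treg measure behind the sample size is biased by the Section 8 statistics.* Section 7.3 already gives flow-cytometry Treg fold change a geometric mean in its tables.

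**What to change.** - **SAP Section 8:** summarise and plot fold change as the geometric mean ratio to baseline, that is, the back-transformed mean of the log ratios, with a confidence interval where group size allows. This matches what Section 7.3 already requires for Treg fold change in its tables.
- **SAP Section 7.3:** limit the geometric mean to positive quantities, namely counts, percentages and fold change.
- **SAP Sections 7.3 and 8:** report absolute change, and in Section 7.3 its AUC, by mean, SD, median and range, without CV%.
- **SAP Section 4.1 (helpful addition):** list the analytes handled on the log scale.

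The cost is SAP wording and table and figure shells. No data collection or site conduct changes.

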**Table 9. Definition of Biomarker Endpoints**

Measure	Definitions	Analysis Timepoint
FC	Mean change from baseline in fecal calprotectin	CCI
hs-CRP	Mean change from baseline in high sensitivity C-reactive protein levels	
sCD25	Mean change from baseline in sCD25	
IL-5	Mean change from baseline in IL-5	
IFN- $\gamma$	Mean change from baseline in IFN- $\gamma$	
IL-1	Mean change from baseline in IL-1	
IL-2	Mean change from baseline in IL-2	
IL-4	Mean change from baseline in IL-4	
IL-6	Mean change from baseline in IL-6	
IL-8	Mean change from baseline in IL-8	
IL-10	Mean change from baseline in IL-10	
IL12p70	Mean change from baseline in IL12p70	
IL-13	Mean change from baseline in IL-13	
TNF-a	Mean change from baseline in TNF-a	
FOXP3	Mean change from baseline in TSDR FOXP3 Assay (Treg cells) (% and cells/ $\mu$ l)	
CD4	Mean change from baseline in TSDR CD4 Assay (CD4 T cells) (% and cells/ $\mu$ l)	

## 9 SAFETY ANALYSES

The safety analyses will be performed using the SAF. The safety parameters will include treatment-emergent AEs (TEAEs) and treatment-emergent serious AEs (TESAEs), vital sign measurements, electrocardiogram (ECG) findings, physical examination findings, and clinical laboratory values. The primary safety analysis will include all data available for all subjects at the time of the primary efficacy analysis data snapshot at **CCI**. Safety will be evaluated via descriptive statistics. No inferential testing for statistical significance will be performed.

### 9.1 ADVERSE EVENTS

#### 9.1.1 ADVERSE EVENT CODING

All AEs will be listed and classified according to the MedDRA, including system organ class (SOC) and PT.

#### 9.1.2 ADVERSE EVENT SEVERITY

The severity of AEs will be graded according to the National Cancer Institute Common Terminology Criteria for AEs (NCI CTCAE) version 5.0 (27 November 2017). The general categories for each grade are presented in **Table 10**.

**Table 10. Adverse Event Severity Grading**

Grade	Severity	Alternate Description
1	Mild	Asymptomatic or mild symptoms; clinical or diagnostic observations only; intervention not indicated
2	Moderate	Minimal; local or non-invasive intervention indicated; limiting age-appropriate instrumental activities of daily living
3	Severe	Severe or medically significant but not immediately life-threatening; hospitalization or prolongation of hospitalization indicated; disabling; limiting self-care activities of daily living
4	Very severe, life-threatening, or disabling	Life-threatening consequences; urgent intervention indicated
5	Death related to adverse event	Death related to adverse event

#### 9.1.3 RELATIONSHIP OF ADVERSE EVENT TO STUDY TREATMENT

The relationship of the AE to study treatment will be assessed by the investigator to be not related or related. If the investigator's opinion of not related to study drug for an SAE is given, an alternative cause of the event such as underlying disease(s), concomitant therapy, and other risk factors must be provided.

#### 9.1.4 SERIOUS ADVERSE EVENTS

SAEs will be identified and captured as SAEs if AEs met the definitions of SAEs that were specified in the study protocol (protocol section 7.6.1.1).

#### 9.1.5 TREATMENT-EMERGENT ADVERSE EVENTS

AEs will be defined as treatment-emergent if they are newly occurring or worsen following exposure to study treatment. All AEs reported following exposure to study treatment are considered TEAEs.

TEAE are defined as 1 or both of the following:

- AE onset date  $\geq$  1st study treatment start date/time; or
- AE onset date  $<$  1st study treatment start date/time and either:
  - The severity worsened on or after the 1st study treatment start date/time; or
  - The event became serious on or after the 1st study start treatment date/time

If the onset date of AE is later than the last dosing date of study treatment, then the event is considered AE in follow-up period.

If the onset date of AE is incomplete and the AE stop date is not prior to the first dosing date of study treatment, then the month and year (or year alone if month is not recorded) of onset determine whether an AE is treatment-emergent. The event is considered treatment-emergent if both of the following 2 criteria are met:

- The AE onset/severity worsened is the same as or after the month and year (or year) of the first dosing date of study treatment, and

- The AE onset/severity worsened is the same as or before the month and year (or year) of the last dosing date of study treatment

An AE with completely missing onset and stop dates, or with the onset date missing and a stop date later than the first dosing date of study treatment, will be considered to be treatment-emergent. In addition, an AE with onset date missing and incomplete stop date with the same or later month and year (or year alone if month is not recorded) as the first dosing date of study treatment will be considered treatment-emergent. All AEs that occur after the safety reporting period and are considered study treatment-related in the opinion of the investigator will also be included. All non-treatment-emergent AEs will be included in the listing.

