7.6.1.3 Reporting Periods for Adverse Events and Serious Adverse Events

The safety reporting period for all AEs and SAEs is from time of study drug randomization through the end of treatment visit or 28 days after the last study treatment, whichever is later. However, all AEs that are the result of a study protocol-specified intervention are to be recorded from the time of informed consent.

All SAEs that occur after the safety reporting period and are considered study treatment-related in the opinion of the Investigator should also be reported to the sponsor.

SAEs will be followed until significant changes return to baseline, the event stabilizes (recovering/resolving) or is no longer considered clinically significant by the investigator, or the patient dies or withdraws consent. All non-serious AEs will be followed through the safety reporting period. Certain non-serious AEs of interest may be followed until resolution, return to baseline, or study closure.

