#### 9.1.6 SUMMARIES OF TREATMENT-EMERGENT ADVERSE EVENTS

TEAEs will be summarized by period based on the SAF.

A brief, high-level summary table will be presented to provide the number and percentage of subjects experiencing any TEAEs, any severe TEAEs, any drug-related TEAEs, any TESAEs, any drug-related TESAEs, any TEAEs leading to study drug interruption or discontinuation, and death.

In addition to the above summary table, summary tables and listings of AE described below will be provided by period.

- Summary of TEAEs by SOC and PT
- Summary of TEAEs by SOC, PT and maximum severity
- Summary of severe (CTCAE Grade  $\geq 3$ ) TEAEs by SOC and PT
- Summary of related TEAEs to Study Treatment by SOC and PT
- Summary of TEAEs of Clinical Interest by SOC and PT
- Summary of related AEs to Study Procedure by SOC and PT
- Summary of serious TEAEs by SOC and PT
- Summary of TEAEs Leading to Premature Discontinuation by SOC and PT
- Summary of related TEAEs to Study Treatment by SOC and PT
- Summary of related Serious AEs to Study Procedure by SOC and PT
- Listing of all AEs
- Listing of serious TEAEs and death
- Listing of TEAEs leading to study drug interruption or discontinuation

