### 12 CONTINUED BLINDED TREATMENT AND OPEN-LABEL ANALYSIS

Any efficacy, safety, PK, and PD data assessments that are completed during safety follow-up, CBT and OL phase will be analyzed and summary tables will be provided.

Safety data will be analyzed based on the methods described in [Section 9](#) PK and PD data will be analyzed based on the methods described in [Section 7](#). Immunogenicity assessments outlined in [Section 7.2](#) may also be further analyzed during the CBT and OL phase. Efficacy endpoints that are assessed in the CBT and OL phase will be analyzed based on the methods described in [Section 6.2](#). All data for the CBT and OL phase will be summarized up until [CCI](#) or until subject's discontinuation from the study.

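### SAP 9.1.5 is inconsistent for adverse events starting after the last dose: an incomplete onset date can remove treatment-emergent status that a full date keeps, and the period boundaries are undefined

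*SAP*

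**What the plan says.** SAP 9.1.5 opens with a definition that has no end date: "All AEs reported following exposure to study treatment are considered TEAEs". The bullets that follow ask only for onset at or after the first treatment, or for an earlier event that later worsens or becomes serious. Protocol 9.3.7.2 also sets no upper limit.

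Two further rules in SAP 9.1.5 refer to the last dose:

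- A label: "If the onset date of AE is later than the last dosing date of study treatment, then the event is considered AE in follow-up period".
- A condition for incomplete onset dates. To be treatment-emergent, the onset or worsening must also be "the same as or before the month and year (or year) of the last dosing date of study treatment".

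The section adds: "All AEs that occur after the safety reporting period and are considered study treatment-related in the opinion of the investigator will also be included". Events classed as not treatment-emergent appear in the listing only.

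SAP 9.1.6 then says "TEAEs will be summarized by period based on the SAF". Neither section says where one period ends and the next begins. SAP 12 states that "safety, PK, and PD data assessments that are completed during safety follow-up, CBT and OL phase will be analyzed", which names safety follow-up alongside the continued blinded (CBT) and open-label (OL) phases.

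On the protocol side, the primary endpoint (2.2.1) includes TEAEs and serious TEAEs through Week 12. The primary safety analysis (9.3.7) takes all available data through Week 12. Adverse events are collected (7.6.1.3) from randomization "through the end of treatment visit or 28 days after the last study treatment, whichever is later".

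**The concern.** TEAE incidence through Week 12 is part of the primary endpoint, so the rule deciding which events count should give one answer per event. Here the answer depends on how completely the onset date was recorded, and the bound that causes this appears nowhere else in either document.

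The follow-up label begins the day after the last dose, which can be well before Week 12. Subjects with a dose-limiting toxicity (DLT) or a drug-related Grade 3 or higher event stop dosing (protocol 3.1.5 and 3.1.7), while protocol 3.1.4 encourages dosed subjects to complete all IBT visits. All their later events would carry the label. If the tables place labelled events in a separate follow-up period, the IBT column would be least complete for the subjects who stopped for toxicity. The planned cohort has 8 active subjects (protocol 9.1). One subject whose only qualifying event is moved changes the incidence by 1/8 = 12.5 percentage points.

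**Working it through.** The plan states no figure to reproduce, because this is a classification rule. The check applies the rules literally.

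**Step 1: one event, four ways of recording it.** Take a last dose on 30 May and an onset on 2 June.

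- Full date: meets the main definition, so it is a TEAE, with the follow-up label.
- Month only (June): June is later than May, so the second partial-date condition fails. It is not a TEAE and goes to the listing only.
- Month only, after the general imputation in SAP 4.1 (missing day set to the 15th): 15 June meets the main definition, so it is a TEAE. The SAP does not say which rule takes precedence.
- Onset and stop dates both wholly missing: SAP 9.1.5 counts it as a TEAE. Knowing less about the date keeps the event in.

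**Step 2: share of incomplete dates affected.** Assumptions: the last dose is equally likely on any day of a 365-day year, and onset is uniform over the 28 days after it. An onset k days after the last dose falls in a later month when the last dose is on one of the last k days of its month. That gives k dates per month, for k up to 28.

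- Month-only dates: 12 × (1 + 2 + … + 28) / (28 × 365) = 12 × 406 / 10,220 = 47.7% lose TEAE status.
- Year-only dates: 406 / 10,220 = 4.0% lose it.
- Full dates: 0% lose it; all receive the follow-up label.

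If the partial-date bound is moved to the end of the protocol reporting period, all three shares are 0% within these 28 days.

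**Step 3: days before Week 12 that carry the follow-up label.** For a last dose on study day L, the labelled days up to Day 85 number 85 − L. The last scheduled IBT dosing day is redacted, so L is an assumption.

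| Last dose (assumed) | Labelled days to Day 85 | Share of 85 days |
|---|---|---|
| Day 1 | 84 | 99% |
| Day 29 | 56 | 66% |
| Day 43 | 42 | 49% |
| Day 57 | 28 | 33% |
| Day 71 | 14 | 16% |
| Day 78 | 7 | 8% |
| Day 85 or later | 0 | 0% |

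The early rows apply only to subjects who stop drug but stay under observation to Day 85. The last row applies to subjects entering CBT or OL, who are dosed again on Day 85 (protocol 6.4.1 and 6.4.2), if the last dosing date is read study-wide. If it is read per phase, their events after the last IBT dose are labelled too. The SAP does not say which reading is meant.

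**Step 4: which period receives a labelled TEAE.** SAP 5.6 ends IBT exposure at the last IBT visit, which suggests that IBT does not close at the last dose. SAP 9.1.5 labels events from the day after the last dose as follow-up, and SAP 12 treats safety follow-up as something to tabulate. The same days can therefore count as IBT exposure while their events are labelled follow-up.

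**The case against.** The best defence is that the follow-up label and TEAE status are compatible. The SAP never says that a labelled event stops being a TEAE, and its main definition says the contrary. Protocol 9.3.7 takes all data through Week 12, SAP 9 takes all data at the snapshot, and follow-up data are tabulated. The partial-date rule touches only incomplete onset dates in a later month or year, the documents give no frequency for these, and the events remain listed. Safety analyses are descriptive, without testing. DLTs have their own definition and window and do not depend on the label. Subjects who terminate early have a visit about 28 days after the last dose, and collection ends around then, so the longest stretches in the table do not apply to them.

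All of this stands against a stronger reading. A reader might infer that the SAP drops adverse events after the last dose in general, or that the primary endpoint is misallocated as written. The documents support neither: fully dated events keep TEAE status, and no text removes labelled events from the Week 12 summary. Nor can a fixed share of the Week 12 window be put on the problem for completers, because the last IBT dosing day is redacted.

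The defence does not answer two things. The partial-date bound contradicts the definition in its own section. And with the periods undefined, a programmer could reasonably place labelled TEAEs outside the IBT column.

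**Conclusion.** The point holds as an internal inconsistency in SAP 9.1.5, with two parts of different strength.

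- **Certain:** an event with an incomplete onset date in a month or year after that of the last dose is classed as not treatment-emergent, although the same event with a full date is a TEAE. Under the uniformity assumptions, this affects 47.7% of month-only and 4.0% of year-only onsets in the 28 days after the last dose. These are shares of incomplete dates, not of all events.
- **A risk:** TEAEs before Week 12 that start after the last dose could be tabulated outside the IBT or Week 12 summary. This concerns subjects who stop drug early and, if the last dose is taken per phase, also completers after their last IBT dose. Its size depends on the redacted dosing day and on how the undefined periods are programmed.

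SAP 14, which lists changes from the protocol, mentions neither part. Since the rule governs a component of the primary endpoint and is cheap to correct, it should be corrected before database lock.

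**What to change.** 1. Replace the partial-date upper bound with the end of the protocol safety reporting period: the later of the end of treatment visit and 28 days after the last dose. Keep the inclusion of related events after that period.
2. State that this rule takes precedence over the 15th-of-month imputation in SAP 4.1 when TEAE status is decided.
3. Define the periods, and assign each TEAE to IBT, CBT or OL by the first-dose date of each phase. Every TEAE from first dose through Week 12, or up to the first CBT or OL dose, then counts in the primary summary whether or not dosing has stopped.
4. Limit the follow-up label to events after that point, and say whether the last dosing date is per phase or study-wide wherever it is used.

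Do not end TEAEs at last dose plus 28 days alone. A subject dosed only on Day 1 who attends to Day 85 would then lose Days 30 to 85 (85 − 30 + 1 = 56 days), all inside the primary endpoint window.

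The cost is SAP wording and a derivation change, with no new data.
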